4.2 Study Stages and Treatment Design

There are four stages to this study, defined as periods:

- Screening Period (-28d): patients undergo screening assessments to determine if they are eligible for the study
- Ferumoxytol (FMX) Period (Day 1 Day 2): patients receive ferumoxytol (FMX) infusion and undergo required FMX-MRI scans prior to receiving MM-398.
- MM-398 Treatment Period (C1D1 progression of disease): patients receive an MM-398 dose of 60 mg/m² every 2 weeks, which should be dose escalated to 80 mg/m² every 2 weeks in subsequent doses depending on patient tolerance, other required assessments, and undergo a post-treatment (MM-398) multiple pass core biopsy

• Follow Up Period (+30d from last dose): patients return to clinic 30 days following the last dose of MM-398 for final safety assessments

For all enrolled patients, a single dose of 5 mg/kg of ferumoxytol will be administered at Day 1 during the ferumoxytol period by intravenous infusion in 50-200 mL of 0.9% sodium chloride or 5% dextrose over a minimum period of 15 minutes following dilution. The total single dose will not exceed 510mg, the maximum approved single dose of ferumoxytol.

MM-398 will be administered by intravenous (IV) infusion over 90 minutes at a dose of 60 mg/m² every two weeks. The MM-398 period (C1D1) should begin within 7 days of the ferumoxytol infusion. The dose of MM-398 should be escalated to 80 mg/m² every two weeks depending on patient tolerance.

All patients will be treated until disease progression (see section 7.1.6.2) or unacceptable toxicity.

Enrollment and Treatment

Between 12 and 20 patients will be enrolled in this the Pilot Phase of the study. The Expansion Phase will enroll up to 30 evaluable patients, in three cohorts. The total enrollment for the study will be approximately 45 patients.

Patients receiving ferumoxytol and not completing all assessments and/or those who do not have evaluable FMX MR images, may still proceed to the MM-398 treatment phase; however additional patients may be enrolled to ensure that adequate MRI data are collected to achieve the objectives of the study. In addition, in order to be considered evaluable from a pharmacodynamic standpoint for the Expansion Phase, patients must have received MM-398 and completed at least one CT scan at the 8-week post-treatment time point.

5 Patient Selection and Discontinuation

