6.1.6.1 Hematologic Toxicities

Prior to each MM-398 dosing, patients must have:

- ANC $\geq 1500/\text{mm}^3$
- Platelet count $\geq 100,000/\text{mm}^3$

Treatment should be delayed to allow sufficient time for recovery, and upon recovery, treatment should be administered according to the guidelines in the tables below. If the patient had febrile neutropenia, the ANC must have resolved to $\geq 1500/\text{mm}^3$ and the patient must have recovered from infection.

			Modification	
Worst CTCAE Grade	ANC Levels (cells/mm ³)	Occurrence	MM-398 adjustment in patients receiving 60 mg/m ² (and have not been escalated to 80 mg/m ²)	MM-398 adjustment in patients receiving 80 mg/m ² (if dose escalated from 60 mg/m ²)
Grade 1 or 2	1000-1999	Any	Same as previous dose	Same as previous dose
		First	50 mg/m^2	60 mg/m^2
Grade 3 or 4	<1000	Second	40 mg/m^2	50 mg/m^2
		Third	Discontinue from MM-398	Discontinue from MM-398

 Table 7:
 MM-398 Dose Modifications for Neutrophil Count

		Modification	
Worst CTCAE Grade	Occurrence	MM-398 adjustment in patients receiving 60 mg/m ² (and have not been escalated to 80 mg/m ²)	MM-398 adjustment in patients receiving 80 mg/m ² (if dose escalated from 60 mg/m ²)
Grade 1 or 2	Any	Same as previous dose	Same as previous dose
	First	50 mg/m^2	60 mg/m^2
Grade 3 or 4	Second	40 mg/m^2	50 mg/m^2
	Third	Discontinue from MM-398	Discontinue from MM-398

Table 8: MM-398 Dose Modifications for Other Hematologic Toxicities

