8.1 Pilot Phase (Closed)

PILOT PHASE SCHEDULE OF ASSESSMENTS REMOVED (MM-398-01-01-02 Version 3.0). This portion of the trial has been completed and the schedule of assessments has been removed from this version of the protocol to reduce confusion during operation of Expansion phase.

Ð	
0	
GR	
IPSEN	

Expansion Phase 8.2

	Screening Period	Ferumoxytol (FMX)Period	oxytol Period				MM-398	MM-398 Treatment Period	nt Period		Follow Up Period
Procedure	-28d	Day 1	Day 2	5	ycle 1 ²³	Cycle 1 ²³ , 2, and 3	d 3	Additional Cycles (every 1 month) ²⁸	al Cycles month) ²⁸	Every 8w	+30d ²²
		•		D1	D3	D8	D15	D1	D15	arter 1 ²² dose	
Informed consent	\mathbf{X}^1										
Medical history	\mathbf{X}^1										
Demographics	\mathbf{X}^{1}										
Physical exam	\mathbf{X}^2			Х				Х			X
Vital signs	X^2	X^3		Х		Х	Х	Х	Х		Х
ECOG PS	\mathbf{X}^2			Х				Х			Х
CBC	\mathbf{X}^2			Х		Х	Х	Х	Х		Х
Serum chemistry ²¹	$X^{2,16}$			Х		Х	Х	X^{16}	Х		X^{16}
UGT1A1*28	$X^{1,17}$										
Coagulation profile ²¹	\mathbf{X}^2			Х				Х			Х
Urinalysis	\mathbf{X}^2										Х
Pregnancy test	\mathbf{X}^2										Х
ECG	$\mathbf{X}^{1,4}$										X^4
FMX-MRI		ςX	X^{6}				\mathbf{X}^7				
Ferumoxytol infusion		X^{25}									
Tumor biopsy ⁸					X^9						
Archived tissue ¹⁰	Х										
Plasma for PK				X^{11}	X^{12}	X^{13}	X^{14}				Х
Biomarker analysis ^{18,21}				X^{14}				Х			Х
Concomitant meds	\mathbf{X}^{1}	Х	Х	Х		Х	Х	Х	Х		Х
MM-398 dosing ¹⁵				Х			Х	Х	Х		
AE reporting						Contin	uous Mc	Continuous Monitoring			
Disease evaluation	$X^{1,24}$									X^{20}	${ m X}^{19}$
¹ Procedures to be completed within 28 days of ferumoxytol dose	1 within 28 days	of ferumox;	ytol dose								

² Procedures to be completed within 7 days of ferumoxytol dose

³ Body weight to be collected within 7 days of ferumoxytol dose

⁴ Two independent readings at least 1 minute apart ⁵ Procedure completed at Cycle 2 only

 6 One reading prior to the start of the MM-398 infusion and one reading post infusion of MM-398 is required 7 Two FMX-MRI collected as outlined in section 7.4 and Table 14 and Table 15

 8 One MRI at 24 h (16-24 hour window) except Scan Group 2, who will undergo 2 repeat scans at the 24 h timepoint 9 For Scan Group 1 only, one MRI scan will be performed during Cycle 1 only (±1 day)

Page 57 of 74

- ¹⁰ Biopsy required for Cohorts 1 and 2, as well as Cohort 3 patients with extracranial disease that can be safely biopsied
 - ¹¹ Post-Treatment Biopsy collected 72h post C1D1 MM-398 infusion

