7 GENERAL STATISTICAL METHODS

7.1 General Methodology

Categorical/qualitative data will be summarized using the number of non-missing observations, frequency counts and percentages. All percentages will be presented as one-decimal point, unless otherwise specified. Percentages equal to 100 will be presented as 100% and percentages will not be presented for zero frequencies.

For continuous variables, descriptive statistics will include the number of non-missing observations (n), mean, standard deviation, median, minimum and maximum. Missing data will be counted but not included in percentage calculations. Where applicable, the same number of decimal places as in the raw data will be presented when reporting minimum and maximum, 1 more decimal place than in the raw data will be presented when reporting mean and median, and standard deviation.

Unless otherwise specified, patients will be counted only once in each tabular summary (e.g. each parameter & visit combination). Reported data that are excluded from tables, e.g. patients excluded from the corresponding analysis population or extraneous measurements (e.g. repeat assessments), will be included in the patient listings.

The pre-treatment period is the time from informed consent to the date of first study drug administration of ferumoxytol or MM-398 respectively. On-treatment period for ferumoxytol is defined as time from ferumoxytol treatment administration to prior to MM-398 administration or within 30 days from date of ferumoxytol termination if patient didn't receive MM-398. The on-treatment period for MM-398 is defined as time from the first administration of MM-398 to 30

days after date of MM-398 termination. Observations recorded on the same date of the first administration of study drug will be considered as on-treatment, unless otherwise indicated by collection time. The post-treatment period is the time following 30 days after the last administration of study drug.

In general, the patient listings will be sorted by phase, patient number and assessment date (and time) if applicable.

For patients who received study drug the reference start date (RFSTDT) is the date of MM-398 administration. Study day is computed as:

- (event/visit date - RFSTDT), if event/visit date < RFSTDT
- (event/visit date - RFSTDT+1), if event/visit date ≥ RFSTDT.

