7.6 Definitions and General Terminology

7.6.1 Baseline

- **Baseline for Ferumoxytol Safety Period**

Baseline for the ferumoxytol period is the last observation before the administration of ferumoxytol.

- **Baseline for MM-398 Safety Period**

Baseline for the MM-398 safety period is the last observation before the first administration of MM-398.

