7.6.3 Study Periods

For the evaluation of safety, assessments will be assigned to study periods. These will be:

- Ferumoxytol safety period: from time of the first dose of ferumoxytol to the time of the first dose of MM-398. If an observation contains a date only, then the corresponding ferumoxytol safety period is the time from the date of the first dose of ferumoxytol to the day before the date of the first administration of MM-398. If the patient does not receive MM-398, the ferumoxytol safety period ends at 30 days after the date of the ferumoxytol dose.
- MM-398 safety period: from time of the first dose of MM-398 to 30 days after the date of the last study drug administration of MM-398. If an observation contains a date only, then the corresponding MM-398 safety period begins on the date of the first administration of MM-398.
- Events/observations will be assigned to study periods based on the start date or date and time if time is available.

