12.2 Clinical Laboratory Evaluations

Scheduled clinical safety laboratory parameters will be summarized. Absolute laboratory values will be summarized by visit. Maximum and minimum change from baseline laboratory data will be summarized. Baseline will be the last measurement taken prior to the first study drug administration of MM-398. Frequency and percent of abnormal laboratory values will be assessed. Shift to most severe toxicity grade will be summarized. These include:

- **Hematology:** hemoglobin, hematocrit, leukocytes, differential white blood cell count, absolute neutrophil count, platelets.
- **Chemistry:** sodium, potassium, chloride, bicarbonate, alkaline phosphatase, ALT (SGPT), AST (SGOT), uric acid, blood urea nitrogen, creatinine, LDH, glucose (random), calcium, magnesium, phosphate, total bilirubin, direct bilirubin, total protein, albumin.
- **Urinalysis:** A urinalysis will include descriptions of color and clarity; pH; specific gravity; and analyses of blood, glucose, ketones and total protein. A microscopic examination of the urine, to include WBC, RBC, bacteria and casts will be performed if the urinalysis is abnormal.

Abnormal lab values will be classified as low (lower than normal limit), normal (within normal range) and high (> upper normal limit). Laboratory values will also be assessed according to NCI CTCAE Version 4.0 or higher, where possible. Abnormal lab values will be flagged (Low [L],

High, [H], abnormal clinically significant [C],) where applicable in the listing. Any unscheduled laboratory assessments will be flagged [U] in the listing.

In addition, a separate listing will be created for all grade 3 and higher post-baseline laboratory observations and any out-of-range values that are identified by the investigator as being clinically significant.

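### SAP 7.1 and 7.6.3 place untimed Cycle 1 Day 1 laboratory values in the MM-398 period, which conflicts with the baseline definitions in SAP 7.6.1 and 12.2

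*SAP*

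**What the plan says.** Two SAP sections decide which period a dosing-day record belongs to.

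- SAP 7.1: "The on-treatment period for MM-398 is defined as time from the first administration of MM-398 to 30" days after MM-398 ends. For records dated on the dosing day it adds: "Observations recorded on the same date of the first administration of study drug will be considered as on-treatment, unless otherwise indicated by collection time".
- SAP 7.6.3: if a record carries a date but no time, "then the corresponding MM-398 safety period begins on the date of the first administration of MM-398".

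Two SAP sections define baseline, and neither says what to do with an untimed record from the dosing day.

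- SAP 7.6.1: "Baseline for the MM-398 safety period is the last observation before the first administration of MM-398".
- SAP 12.2, for laboratory data: "Baseline will be the last measurement taken prior to the first study drug administration of MM-398". Protocol 10.7 gives the same definition.

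The Protocol fixes when the samples are taken.

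- Section 6.1.6.1 opens its list of count thresholds with "Prior to each MM-398 dosing, patients must have", then names ANC (at least 1500/mm³) and platelets (at least 100,000/mm³).
- The Expansion Phase schedule in section 8.2 has blood count, chemistry, coagulation and ECOG at screening and again on Day 1 of Cycle 1. None of these is scheduled in the ferumoxytol period. The screening entries carry the footnote "Procedures to be completed within 7 days of ferumoxytol dose".
- Section 4.2: "The MM-398 period (C1D1) should begin within 7 days of the ferumoxytol infusion".

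**The concern.** Treating a same-day record as on-treatment is a sensible default for adverse events. It does not suit a blood sample taken to decide whether the patient may be dosed. Such a sample is pre-dose, and it is the natural baseline for MM-398.

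SAP 12.2 plans maximum and minimum change from baseline and the shift to the most severe grade. If an untimed Day 1 value counts as an MM-398-period value, a measurement made before the drug enters the summaries of what happened after it. If the Day 1 value is also lost as baseline, those summaries start from screening, and anything that changed between screening and Day 1, including after ferumoxytol, is credited to MM-398.

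Day 1 of Cycle 1 also has the only scheduled blood count, chemistry and coagulation after ferumoxytol and before MM-398. Moving it into the MM-398 period leaves the ferumoxytol period with no scheduled laboratory data, although SAP 12 presents safety by these periods. Finally, baseline could differ between patients merely because one site entered a time and another did not.

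**Working it through.** The documents give no figure for the gap between baseline and dose, so there is none to reproduce. The check has three parts.

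**1. What happens to an untimed blood count drawn before dosing on Cycle 1 Day 1.** The texts allow three treatments:

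- *The same-day rule governs both period and baseline.* The value is an MM-398-period value, and baseline is the screening value.
- *The same-day rule governs the period and the baseline definition governs baseline.* The sample was in fact taken before MM-398, so it meets 7.6.1 and 12.2 and becomes baseline, yet 7.1 and 7.6.3 also place it in the MM-398 period. One record is then both baseline and on-treatment. If it is summarised as such, it contributes a change of value − value = 0, so the maximum change cannot be below 0 and the minimum change cannot be above 0.
- *The sample is treated as pre-dose throughout.* Baseline is the Day 1 value and nothing pre-dose enters the MM-398 summaries. No SAP sentence provides for this unless a time is recorded.

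**2. Age of the fallback baseline (first treatment above).**

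- Screening to ferumoxytol: 0 to 7 days (Protocol 8.2, footnote 2).
- Ferumoxytol to Cycle 1 Day 1: 1 to 7 days (Protocol 4.2). The lower limit of 1 assumes that MM-398 starts no earlier than the day after ferumoxytol, since the Day 2 scan precedes it.
- Shortest gap: 0 + 1 = 1 day. Longest gap: 7 + 7 = 14 days.
- With the Day 1 value as baseline the gap is 0 days.

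The 7-day limit to Cycle 1 Day 1 is worded as a recommendation, and the Protocol allows MM-398 to be held after a ferumoxytol reaction, so a longer gap is possible. The figure applies to the Expansion Phase; the Pilot schedule has been removed from this protocol version.

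**3. Largest grade that a compliant pre-dose count can add.** The thresholds are in Protocol 6.1.6.1 and the grades in SAP Appendix A.

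- ANC of at least 1500/mm³ = 1.5 × 10⁹/L. Grade 1 runs from 1.5 × 10⁹/L up to the lower limit of normal, so the value is Grade 1 at most.
- Platelets of at least 100,000/mm³ = 100 × 10⁹/L. Grade 1 runs from 75 × 10⁹/L up to the lower limit of normal, so the value is Grade 1 at most.

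Haemoglobin, chemistry and coagulation have no such threshold on the dosing day, so this ceiling does not extend to them.

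**The case against.** The strongest reply is that the same-day sentence allocates records to periods and does not define baseline. A blood count that had to be seen before dosing was taken before dosing, so it literally meets 7.6.1 and 12.2. This stands against any claim that the SAP sets baseline at screening: the fallback is an inference from reading the sections together. It does not remove the problem, because 7.1 and 7.6.3 still expressly place the same record in the MM-398 period.

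The SAP also provides for collection times, and a timed pre-dose sample is handled correctly. A schedule footnote allows samples 2 days either side of the planned date, and one drawn on an earlier date escapes the rule. Both points stand and limit the reach.

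A reader might infer more than the documents support:

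- *That all of the roughly 30 Expansion Phase patients are affected.* That is a ceiling. The documents do not say whether the case report form records sample times.
- *That every Day 1 assessment is pre-dose by design.* Only ANC and platelets are expressly required before dosing. Chemistry, coagulation and ECOG share the visit but are not labelled pre-dose.
- *That one can put a probability on the pre-dose value being the worst.* That would treat pre- and post-dose values as interchangeable. Counts fall on treatment: Protocol Table 4 reports Grade 3 or higher neutrophil decreases in 16% (monotherapy) and 20% (combination) of MM-398 patients.
- *That vital signs and ferumoxytol Day 1 need the same remedy.* On ferumoxytol Day 1 only vital signs are scheduled among these assessments. Protocol 6.2.3 has blood pressure and pulse monitored during the infusion and for at least 30 minutes afterwards, so an untimed reading cannot be presumed pre-dose.

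**Conclusion.** The point holds as a stated rule that misclassifies some records and conflicts with the baseline definitions. Untimed Cycle 1 Day 1 blood count, chemistry and coagulation records dated on the day of first MM-398 would be counted in the MM-398 period. If the same rule also decides baseline, baseline is about 1 to 14 days old instead of same-day.

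This rests on two conditions: no collection time is recorded, and the sample is drawn on the dosing date. How many patients meet both cannot be learned from the documents.

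The consequence is modest. The study is descriptive, and no efficacy endpoint or dosing decision depends on the rule. A compliant pre-dose ANC or platelet value cannot produce a spurious Grade 2 or higher worst value. The laboratory change and shift tables are the most exposed. For ECOG, only the baseline characteristic and the period assignment are touched, since no change from baseline is planned.

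**What to change.** Add one sentence to SAP 7.1 and cross-reference it in 7.6.1, 7.6.3 and 12.2: scheduled Cycle 1 Day 1 blood count, chemistry and coagulation records without a collection time (and ECOG, if done before dosing) are treated as pre-dose and are eligible as the MM-398 baseline. Adverse events, unscheduled records and vital signs keep the existing same-day default.

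The change affects neither data collection nor patient care and should be made before the tables are programmed. Its cost is that an occasional untimed sample actually drawn after dosing on Cycle 1 Day 1 could be read as baseline.

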7.2 Methods for Missing Data, Multiple Observations, and Outliers

7.2.1 General Considerations

In general, data will be analyzed as received from the clinical database. Hence, missing measurements including those caused by dropouts will not be imputed.

7.2.2 Partial and Missing Dates

Missing or partially missing date in the following situations will be imputed for purposes of analysis.

Partial Dates for Death: It is anticipated that nearly all death dates will be completely captured. Any partially missing date of this type will be queried before statistical analyses are performed. In cases of partial dates, death date may be known to month and year. For the primary analysis, date recorded as month and year only will be imputed to the later date of: 1st of the corresponding month and last known alive date plus one day.

Partial/Missing Dates for Study-Related Visits or Procedures: It is anticipated that all study-related visit and procedure dates entered into the clinical study database will be complete (i.e. day, month, year are all recorded) and accurate. Any missing or partially missing date of this type will be queried before statistical analyses are performed. If the day, month, or year is still unknown, then the dates will be imputed as follows for purposes of analysis:

- If the day of the visit or procedure date is missing, then take the previous visit and add the number of days to the next visit according to the visit schedule.
- If the month of the visit or procedure date is missing, then take the previous visit and add the number of months to the next visit according to the visit schedule.
- If the year of the visit or procedure date is missing, then the year will be queried. If the year is unknown, no imputation of year will take place.

Partial/Missing Start Date for Adverse Events or concomitant medications: Missing adverse event (AE) dates will be imputed for the purpose of classification as treatment emergent or not. For any adverse event or concomitant medication that has a missing or incomplete start date, a query will be issued to capture the full date. If only a partial date is reported for the start of an AE or medication, a complete date will be estimated using the following algorithm:

- Completely missing (i.e., missing the year, month and day): the date of first study drug administration. Therefore, any such AE would be treatment emergent, and any such medication would be concomitant.
- Only the year is reported (i.e., missing the month and day): earlier date of '1 January' and the date of first study drug administration.
- The year and month are reported (i.e., missing the day): earlier date of first day of the month and the date of first study drug administration.

Partial/Missing End Date for Adverse Events or concomitant medications: If only a partial date is reported for the end of an AE or medication, a complete date will be estimated:

- Completely missing: then the AE or medication will be considered ongoing at the end of the study.
- Only the year is reported: '31 December' will be used, unless this is after the date of final follow-up, in which case the AE or medication will be considered ongoing at the end of the study.
- The year and month are reported: the last day of the month will be used, unless this is after the date of final follow-up, in which case the AE or medication will be considered ongoing at the end of the study.

Partial/Missing start date of post study drug anticancer therapies: If only a partial date is reported for the start date of post study drug anticancer therapies, a complete date will be estimated:

- Completely missing (i.e., missing the year, month and day): the date of last study drug administration+1.
- Only the year is reported: later date of '1 January' and the date of last study drug administration+1.
- The year and month are reported: later date of first day of the month and the date of last study drug administration +1.

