12.1 Adverse Events

Adverse events will be coded using the MedDRA dictionary. Levels of classification will include primary system organ class and preferred term. In addition, toxicity grading will be assigned according to NCI CTCAE.

General Rules for summarizing AEs:

- (1) An AE will be considered as treatment-emergent (TE) if it begins on or after study drug dosing, starts prior to dosing and increases in grade/severity or seriousness after dosing, or starts prior to dosing but the causality changed to “related” after dosing. In case of missing dates, an AE will be considered as treatment-emergent.

- (2) In the event of multiple adverse events being reported by the same patient, the most serious causality (related > not related) will be chosen.
- (3) In the event of multiple occurrences of the same adverse events being reported by the same patient, the maximum intensity (Grade 5 > Grade 4 > Grade 3 > Grade 2 > Grade 1 > missing > not applicable) and the most serious causality (related) will be chosen.
- (4) If a patient experiences the same AE (i.e. same preferred term) more than once, they are only counted once under the count for preferred term.
- (5) If a patient experiences more than one AE in a particular system organ class, they will only be included once in the count for the system organ class, but will appear in the count for each appropriate preferred term within the system organ class (unless it is the same preferred term).
- (6) AEs related to study drug tables include only those AEs with a relationship to study drug of 'related' or if there is a missing relationship on the AE page of the CRF.
- (7) For AE severity the following rules will be applied in determining the counts of AEs:
 - An individual patient who experiences two AEs of the same preferred term of the same severity will be included once in the appropriate severity count for the particular AE.
 - An individual patient who experiences two AEs of the same preferred term but different severity will be included once in the severity count for the higher severity but not in the count for the lesser severity.
 - In the total counts for each severity classification, an individual patient who experiences two AEs of different preferred term of the same severity will be included once in the total for the appropriate severity.

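### The SAP's rule for partial adverse event start dates places events from the dosing month or year before dosing, conflicts with the treatment-emergent definition, and does not say which drug's first dose it means

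*SAP*

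**What the plan says.** SAP 7.2.2 gives the purpose of the rule: "Missing adverse event (AE) dates will be imputed for the purpose of classification as treatment emergent or not". After a query, three cases remain.

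- Nothing known: the date of first study drug is used. "Therefore, any such AE would be treatment emergent, and any such medication would be concomitant".
- Year only: the earlier of 1 January and first study drug.
- Month and year: the "earlier date of first day of the month and the date of first study drug administration".

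SAP 12.1 calls an AE treatment-emergent "if it begins on or after study drug dosing", or if an earlier event worsens or becomes related after dosing. It adds: "In case of missing dates, an AE will be considered as treatment-emergent".

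SAP 7.6.3 assigns events to a ferumoxytol or an MM-398 safety period by start date. For date-only records, "If an observation contains a date only, then the corresponding MM-398 safety period begins on the date of the first administration of MM-398"; the ferumoxytol period ends the day before. SAP 12 presents safety by these periods.

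On which drug counts as first, SAP 7.1 ends the pre-treatment period at the "date of first study drug administration of ferumoxytol or MM-398 respectively", but also states: "For patients who received study drug the reference start date (RFSTDT) is the date of MM-398 administration". Protocol 10.7 counts treatment-emergent events from the first dose of either drug.

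**The concern.** Taking the earlier of two dates caps every imputed start at first dose. Where classification is actually in doubt, in the month or year of dosing, the rule resolves it as pre-dose. That is the reverse of the default for an undated event, so knowing more about an event removes it from the treatment-emergent tables.

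Whether 12.1 repairs this is unclear. Section 7.2.2 uses the word missing for partial dates too, so 12.1 may cover them. Two programmers could flag the same event differently, each with text in support.

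The unnamed anchor drug matters because the two drugs have separate safety populations and periods. Safety of MM-398 in the presence of ferumoxytol is a secondary objective of all phases, and the imputed date decides which period an event is counted in.

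**Working it through.** The plan states no figure here, so the check applies the rule directly:

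imputed start = min(1st of the month or 1 January, first-dose date).

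**Example A** (assumed dates: ferumoxytol 15 Jun 2016, MM-398 20 Jun 2016; SAP 3.1 allows up to 7 days between them)

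| Recorded | Ferumoxytol anchor | MM-398 anchor | Result |
|---|---|---|---|
| Jun 2016 | 1 Jun | 1 Jun | before both drugs |
| 2016 | 1 Jan | 1 Jan | before both drugs |
| Sep 2016 | 15 Jun | 20 Jun | treatment-emergent either way; ferumoxytol or MM-398 period |

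The September event is dated at least 78 days early (15 Jun to 1 Sep) or 73 days early (20 Jun to 1 Sep).

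**Example B** (ferumoxytol 28 Jun, MM-398 3 Jul 2016). Jul 2016 becomes 28 Jun or 1 Jul. Both lie in the ferumoxytol period, although 29 of the 31 July days are on or after the MM-398 start.

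**Share of truly post-dose events dated before dosing.** Assume dosing uniform over the 366 days of 2016 and onset uniform over days 0 to W−1.

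- Month-only, W up to 29: an event escapes only if it falls in a later month or dosing was on the 1st. Share = 1 − 6(W+1)/366. W = 14: 1 − 90/366 = 75%. W = 28: 1 − 174/366 = 52.5%.
- Month-only, W of 31 or more: a month of length L contributes L(L−1)/2 pre-dated pairs. Over 2016 this is 7×465 + 4×435 + 406 = 5,401, and share = 5,401/(366W). W = 56: 26%. W = 182: 8%.
- Year-only: share = 1 − (W+1)/732, giving 98%, 96%, 92% and 75% for W = 14, 28, 56 and 182.

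A separate enumeration over a 365-day year, with onset 0 to 180 days after dosing, splits the events by type:

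- Month-only, same month as dosing: 5,373 of 5,738 (93.6%) dated before dosing. The exceptions are doses on the 1st.
- Year-only, same year as dosing: 49,594 of 49,775 (99.6%). The exceptions are doses on 1 January.
- Later month or year: all are moved to the first-dose date (60,327 of 60,327 month-only; 16,290 of 16,290 year-only).

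**How often one month holds both first doses.** For a gap of g days the share is (366 − 12g)/366, which is 97% at g = 1 and 77% at g = 7.

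**The case against.** - **The two main complaints partly exclude each other.** If 12.1 covers partial dates, the treatment-emergent flag is restored; if it covers only wholly missing dates, the two sections agree in wording. This is fair. On the first reading, however, 12.1 contradicts the date that 7.2.2 produces, and a date before ferumoxytol belongs to neither 7.6.3 safety period, only to the pre-treatment period of 7.1. On the second, dosing-month events leave the treatment-emergent tables. Neither outcome is sound.
- **Section 12.1 has other routes.** A pre-dated event still qualifies if it worsens or its causality changes to related. True, but an ordinary new event after dosing need do neither.
- **The SAP works per drug, and the reference start date serves only to compute study day.** A per-drug reading is possible, but 7.2.2 does not state it. It would also give one event two start dates: the Sep 2016 event would be 15 Jun for ferumoxytol and 20 Jun for MM-398, and so fall in both periods.
- **Displaced onset has little effect, since no time-to-onset analysis is planned.** Agreed for onset day. Its effect on period assignment remains.
- **The scale is small.** Dates are queried first, onset date is a required AE item in protocol 9.2, the study is descriptive, and the all-AE and SAE summaries and listings keep the events. This stands and limits the importance of the point.

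**Conclusion.** The concern holds. The stated rule defeats its stated purpose. It dates dosing-month and dosing-year events before dosing, with exceptions only for doses on the 1st or on 1 January, and moves every later event back to first-dose day. Its fit with 12.1 is unresolved and its anchor drug is unnamed.

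The percentages describe only events that truly began after dosing and whose dates remain partial after query. They rest on uniform dosing and onset and on the chosen windows. The documents do not say how many such dates there will be; there may be few. No efficacy endpoint is touched. The point is worth correcting before programming because it can change treatment-emergent counts and the split of events between the two drugs.

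**What to change.** Replace the two partial-date bullets for AEs in SAP 7.2.2 with one ordered rule giving one imputed date. Define the anchor as the first ferumoxytol dose, or the first MM-398 dose if no ferumoxytol was given.

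1. Reported month or year before that of the anchor: pre-treatment.
2. Reported month or year contains the first MM-398 dose: impute that date, unless the AE ended before it. This is also the tie-break when both first doses fall in the reported month or year.
3. Otherwise, if it contains the ferumoxytol dose: impute that date, unless the AE ended before it (then pre-treatment).
4. Otherwise, month or year later than the anchor's: impute the 1st of that month or 1 January, not after the AE end date.

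Use this date for the 7.6.3 periods as well. Partial end dates can be tested after their own imputation: 7.2.2 sets them to the last possible day, so an event is excluded only if it must have ended before the dose.

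In Example A this gives: May 2016 pre-treatment; Jun 2016 = 20 Jun; Jun 2016 ending 18 Jun = 15 Jun; Jun 2016 ending 10 Jun pre-treatment; Sep 2016 = 1 Sep. In Example B, Jul 2016 ending 2 Jul becomes 1 Jul, in the ferumoxytol period.

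State in 12.1 that partial dates follow 7.2.2 and that only completely missing dates are treatment-emergent by default. State separately whether concomitant medications, which share these bullets, keep the present rule. Simply replacing earlier with later is not enough: an event known to be from a month before dosing would become treatment-emergent.

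The cost is one SAP paragraph, one sentence in 12.1 and one macro. Treatment-emergent counts may rise slightly, because some true pre-dose events in the dosing month will be included. The tie-break will move some month-only ferumoxytol events to the MM-398 period, and it can apply often, since both first doses share a month in 77% to 97% of patients for gaps of 7 down to 1 day.
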